#### 4.5.2.3. Vision

Vision will be analyzed using the methods described above for overall comfort.

#### 4.5.2.4. Front Surface Deposits

Maximum Front Surface Deposits Over All Follow-up Visits ( $\leq 2$ ,  $> 2$ ) will be summarized at the eye level by treatment using categorical summary statistics for the ITT Population in a table. A one-sided lower 97.5% confidence limit around the difference in " $\leq 2$ " proportions between the Test and Control treatment groups will be constructed using the Newcombe-Wilson score method.

If the lower confidence limit is greater than -10.0% or if no deposits with grade greater than 2 are observed in either treatment group, then the null hypothesis that the Test solution is not noninferior will be rejected, and the Test solution will be statistically successful in this outcome.

#### 4.5.3. Sensitivity Analyses

The four primary endpoints ( $>$ Grade 2 slit-lamp findings, overall comfort, vision, and front surface deposits) will each have the following sensitivity analyses performed:

- **PP Analysis:** the original analyses will be repeated using the PP Population (efficacy endpoints only: overall comfort, vision, and front surface deposits).
- **Best/Worst-Case Imputation Analysis:** each eye with missing values at any scheduled follow-up visit will have their missing values imputed and analyzed twice (analyzed repeating the original analysis using the ITT Population), once using the best- and once using the worst-case scenarios. Following Yan et al. (2009), the worst-case imputation imputes the worst response observed among the test group for the missing responses in the test group, and imputes the best response observed in the control group for the missing responses in control group. The best-case imputation is the reverse of this: impute the best response observed among the test group for the missing responses in the test group, and impute the worst response observed in the control group for the missing responses in control group.

For slit-lamp findings, the best response is "Absent" (i.e. no findings  $>$ Grade 2), and worst is "Present". For overall comfort / vision, the best response is the equivalent to the largest response, and worst is equivalent to the smallest response (scale of 0-100). For

frontal surface deposits, the best response is no grade greater than 2, while the worst is a grade of 2 or greater.

- **Tipping-point Analysis:** If any observed-cases primary efficacy analysis conclusion is different than either the best-case or worst-case imputation conclusion (i.e. the observed-cases primary efficacy analysis concludes non-inferiority, but the worst-case imputation fails to conclude non-inferiority), then an additional tipping-point analysis will be performed for that endpoint using the ITT Population.

The tipping-point analysis will follow the spirit of the algorithms for continuous and binary data, as appropriate, as described in Yan et al. (2009).

**Continuous outcomes** (overall comfort and vision): The tipping point analysis will iteratively (1) impute all missing values in the dataset and then (2) perform the primary analysis (e.g. determine the non-inferiority of test vs. control via an analysis of variance model including the fixed factors of treatment, site, and lens group) on the imputed dataset. Iterations continue until the outcome of the analysis using the imputed dataset results in the opposite conclusion as observed in the observed cases primary analysis.

For example, an observed cases primary analysis that results in the rejection of non-inferiority will iteratively impute better and better scores within the Control group (and worse and worse scores within the Test group), until non-inferiority fails to be rejected.

The algorithm is as follows. For the first iteration: if an eye is missing all scheduled follow-up visits, then their endpoint (i.e. the average over all visits) will be imputed using the observed group (i.e. Test or Control) mean. Otherwise, all visit-specific missing values for the given eye will be imputed using the observed eye-level mean (meaning the average over all observed visits for that eye). This will create the first iteration of the imputed dataset. The primary analysis will then be run on this imputed dataset. If this analysis contradicts the observed cases analysis, then the tipping point has been found, and the imputed dataset will be called the tipping point dataset, and the tipping point analysis is completed.

Otherwise, iterate as follows: for each group, imputed values will be perturbed by 0.005 as either a worsening (i.e. -0.005) or an improvement (i.e. +0.005), depending on the direction of the tipping point, and the primary analysis will be performed on this new imputed dataset. If this analysis contradicts the observed cases analysis, then the tipping point has been found, the imputed dataset will be declared the tipping point dataset, and the tipping point analysis is completed. Otherwise, continue to perturbate the imputed values by increments 0.005 until the tipping point is reached.

The tipping point dataset's group means, and the estimated difference in group means, will be reported.

**Binary outcome** (proportion of eyes with any slit-lamp findings >Grade 2 and proportion of eyes with a maximum degree of front surface deposits grade of  $\leq 2$  at any scheduled follow-up visit.): All missing values will be imputed as some combination of either successes or failures, across all possible combinations. Combinations that result in a tipping point (i.e., a result contrary to what was determined by the primary analysis) will be flagged as such, and displayed as a plot showing the tipping points.

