		
Efficacy Endpoint (2): Vision (at the eye level) averaged over all scheduled follow-up visits as measured via Lens Performance Rating Scale: Vision.
 
Clinical Question: Does BL-3100-NBR03 multi-purpose solution result in non-inferior average vision compared to renu® Advanced Formula multi-purpose solution, when used over the course of 3 months in randomized eyes?

		
Estimand: The difference in group means, between BL-3100-NBR03 and renu®, of [the average (over each follow-up visit) of “vision” for each eye], using all randomized eyes. Missing values will be ignored when computing average vision and, subsequently, the difference in group means.
 
Efficacy Endpoint (3): The proportion of eyes with a maximum degree of front surface deposits grade of <math>\leq 2</math> at any scheduled follow-up visit.
 
Clinical Question: Does BL-3100-NBR03 multi-purpose solution result in a non-inferior proportion of eyes with maximum degree of front surface deposits (grade <math>\leq 2</math>) compared to renu® Advanced Formula multi-purpose solution, when used over the course of 3 months in randomized eyes?
 
Estimand: The difference in group proportion, between BL-3100-NBR03 and renu®, of [the proportion of eyes with a maximum degree of front surface deposits grade of <math>\leq 2</math> across all scheduled follow-up visits], using all randomized eyes. Missing values will be ignored when determining the maximum grade of front surface deposits for each eye and, subsequently, the difference in proportion between groups.

Secondary		
There are no predefined secondary endpoints		
Supportive Effectiveness		
Proportion of subjects treated with BL-3100-NBR03 agreeing with the consumer survey statements.		
Difference in group proportion, between BL-3100-NBR03 and renu®, of subjects agreeing with the consumer survey statements.		
Sensitivity Analyses: Best/worst case imputation analyses using best/worst imputation for primary endpoints.		
Sensitivity Analyses: Tipping-point analyses for primary endpoints.		
Sensitivity Analyses: Primary efficacy endpoints using only subjects without major protocol deviations (i.e. Per-Protocol analysis).		

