#### 4.5.1. Definition of Endpoints

The safety-related endpoint is as follows:

- The proportion of eyes with any slit-lamp findings greater than Grade 2 over all follow-up visits (scheduled and unscheduled).
  - At each follow-up visit, graded slit-lamp findings will be assessed for each eye using Grades 0 through 4. Using only the non-missing observations from all follow-up visits, each eye will be classified with respect to findings greater than Grade 2 at any visit (Absent, Present).

The efficacy-related endpoints are as follows:

- Overall comfort averaged over all scheduled follow-up visits.
  - At each follow-up visit, overall comfort will be assessed for each eye on a scale from 0 to 100, with 100 denoting the most favorable response. For each eye, mean overall comfort over all follow-up visits will be computed as the average of the non-missing values over all scheduled follow-up visits
- Vision averaged over all scheduled follow-up visits.
  - At each follow-up visit, vision will be assessed for each eye on a scale from 0 to 100, with 100 denoting the most favorable response. For each eye, mean vision over all follow-up visits will be computed as the average of the non-missing values over all scheduled follow-up visits.
- The proportion of eyes with a maximum degree of front surface deposits grade of  $\leq 2$  over all scheduled follow-up visits.
  - At each follow-up visit, the degree of front surface deposits will be graded for each eye as 0, 1, 2, 3, or 4. Using only the non-missing observations from scheduled follow-up visits without imputation, each eye will be classified with respect to the maximum grade of front surface deposits ( $\leq 2$ ,  $> 2$ ) observed over all follow-up visits.

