#### 4.5.2. Main Analytical Approach

All contrasts and differences will be calculated as Test – Control. All observations will be treated as independent (e.g. each eye and/or each subject).

##### 4.5.2.1. Graded Slit-Lamp Findings > Grade 2

Greater than Grade 2 findings (Absent, Present) overall all follow-up visits will be summarized at the eye level by treatment using categorical summary statistics for the Safety Population. A one-sided upper 97.5% confidence limit around the difference in “Present” proportions between the Test and Control treatment groups will be constructed using the Newcombe-Wilson score method.

If the upper confidence limit is less than 5.0% or if no findings greater than Grade 2 are observed in either treatment group, then the null hypothesis that the Test solution is not noninferior will be rejected, and the Test solution will be statistically successful in this outcome.

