#### **4.10. Changes to Protocol-Planned Analyses**

Included a tipping point analysis to primary safety endpoint of proportion of eyes with any slit-lamp findings greater than Grade 2 over all follow-up visits. There are no other planned changes to the protocol-planned analyses.

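### SAP 4.5.3 contradicts other SAP sections on three points of the missing-data sensitivity analyses: the tipping-point trigger, the slit-lamp analysis set and the deposits cut-point (minor)

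*SAP*

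**What the plan says.** **Scope.** SAP 4.5.3 opens by naming slit-lamp, comfort, vision and deposits, and says that they "will each have the following sensitivity analyses performed". Only the per-protocol bullet is limited to the efficacy endpoints. SAP Table 2 lists "Sensitivity Analyses: Tipping-point analyses for primary endpoints". The binary tipping-point algorithm in 4.5.3 names slit-lamp. SAP 4.10 gives as the only change from the protocol: "Included a tipping point analysis to primary safety endpoint".

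**Trigger.** The tipping-point analysis is conditional: "If any observed-cases primary efficacy analysis conclusion is different than either the best-case or worst-case imputation conclusion". The example in brackets that follows again refers to the primary efficacy analysis. SAP 4.5.1 keeps slit-lamp apart from the efficacy endpoints, under the line "The safety-related endpoint is as follows".

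**Analysis set.** For best/worst-case imputation, "each eye with missing values at any scheduled follow-up visit will have their missing values imputed and analyzed twice", and the data are "analyzed repeating the original analysis using the ITT Population". The tipping-point bullet also names ITT. The primary slit-lamp analysis in SAP 4.5.2.1 is summarised "using categorical summary statistics for the Safety Population", and SAP Table 4 groups that population by treatment received.

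**Worst response.** The general rule in 4.5.3 imputes the worst value observed in the Test group. Slit-lamp then gets its own pair of responses: best is Absent, worst is Present. For deposits, the best response is no grade above 2 and the worst is grade 2 or higher. SAP 4.5.1 and 4.5.2.4 count grade 2 as success.

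**The concern.** The primary slit-lamp analysis ignores missing values, so the imputation and tipping-point analyses are what show how far missing eyes could change the safety conclusion. If the worst case reverses that conclusion, the tipping-point plot is the next thing a reader needs, and the triggering sentence does not call for it.

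The ITT instruction makes the slit-lamp sensitivity analysis differ from the primary one in two ways at once: the missing values are filled in, and the analysis set changes from dispensed subjects by treatment received to all randomized subjects by assignment. A difference in result could not then be put down to missing data alone.

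The deposits wording places grade 2 in both the best and the worst response, so the imputation rule disagrees with the endpoint it serves.

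**Working it through.** **Inputs.** Slit-lamp rate 0.008 per arm, 300 eyes per arm, margin 5% (SAP 2.2.4, 4.5.2.1). Deposits success rate 0.942, margin -10% (SAP 2.2.3, 4.5.2.4). Enrolment 340 subjects, 1:1, losses up to 10% (SAP 2.2.6), hence 170 subjects or 340 eyes per arm. z = 1.96. How many eyes will be missing, and in which arm, is assumed.

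**Formula.** Newcombe-Wilson upper limit for Test minus Control: (pT - pC) + sqrt[(uT - pT)² + (pC - lC)²], where uT is the upper Wilson limit for Test and lC the lower Wilson limit for Control.

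**The plan's own figure.** Exact enumeration at 300 eyes per arm, 0.008 in each, independent eyes: power 99.94% (stated 99%). It reproduces.

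**1. Can the slit-lamp worst case reverse the conclusion?** Expected events are 0.008 × 340 = 2.7, so take 3 in each arm. Missing Test eyes become Present and missing Control eyes Absent.
- 8 Test eyes imputed: 11/340 v 3/340. pT = 3.24%, uT = 5.70%, pC = 0.88%, lC = 0.30%; upper limit 4.88%, passes.
- 9 Test eyes imputed: 12/340 v 3/340. pT = 3.53%, uT = 6.07%; upper limit 5.25%, fails.
- Losses of 10% in each arm (34 eyes; 0.008 × 306 = 2.4, so 2 observed events): 36/340 v 2/340; upper limit 13.75%, fails.

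Because any missed scheduled visit makes an eye subject to imputation, 4 Test subjects with one missed visit (8 eyes) stay inside the margin in this example and 5 (10 eyes) do not. So a reversal is plausible within the planned losses.

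**2. How much does the analysis set change?** At 10% missing, suppose k of the missing Test subjects were never dispensed (assumption). The Safety Population then drops 2k eyes, all imputed Present on ITT.

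| k | Safety worst case | Upper limit |
|---|---|---|
| 0 (same as ITT) | 36/340 v 2/340 | 13.75% |
| 1 | 34/338 v 2/340 | 13.16% |
| 3 | 30/334 v 2/340 | 11.97% |
| 5 | 26/330 v 2/340 | 10.73% |

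All fail, so the conclusion is the same on either set.

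**3. Deposits.** Under the general rule, the imputed value is the worst one observed in Test. Even if a subject's two eyes always agree, the chance that no observed Test eye exceeds grade 2 is 0.942^153 = 0.01%, so the rule would almost always give a failure despite the wrong cut-point. A different result needs exactly grade 2 to be imputed and then scored as success. With 34 eyes missing per arm and 288 observed successes (0.942 × 306), the lower limit is -3.5% on that reading (322/340 v 322/340) and -14.6% with failures imputed (288/340 v 322/340).

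**4. Lesser point: observed worst v Present.** The two slit-lamp statements conflict only if Test has no finding above Grade 2.
- Independent eyes: 0.992^306 = 8.6%; 0.992^340 = 6.5%.
- A subject's eyes always agree: 0.992^153 = 29%; 0.992^170 = 26%.

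If this happens with 2 Control events and 34 missing Test eyes, the observed-value rule gives 0/340 v 2/340, upper limit 0.6% (passes), and the Present rule gives 34/340 v 2/340, 13.1% (fails).

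**The case against.** The intent on the trigger is not in doubt. The lead-in, Table 2, the binary algorithm and 4.10 all include slit-lamp, and where 4.5.3 means to leave it out, as in the per-protocol bullet, it says so. An analyst would have to set four statements aside to skip the analysis, and the failed worst case would still be reported. This stands, and it is why the point is minor. The condition that starts the analysis nevertheless contradicts the other four statements and should be corrected.

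On the analysis set, SAP 4.1.1 allows exceptions to its default, and 4.5.3 does specify ITT. Randomization and kit dispensing are consecutive steps of one visit (Protocol 6.1.1), so the two sets should nearly coincide. Both arguments are fair and limit the numerical effect. Against them, 4.5.3 says that the original analysis is repeated, and for slit-lamp that analysis is not on ITT. SAP 4.1.2 and Protocol 8.6.8 prescribe ITT missing-data work for the effectiveness endpoints only, and 4.10 declares no change of population.

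On the worst responses, a specific definition normally governs a general one, so Present is the natural reading for slit-lamp. The deposits wording looks like a slip, since the best response already covers grade 2. Both arguments reduce the expected effect. The deposits contradiction itself remains.

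A reader might infer that 4.5.3 applies an efficacy definition of worst response to slit-lamp. It does not: slit-lamp has its own responses, in the right direction.

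**Conclusion.** The point holds as three internal contradictions in SAP 4.5.3, plus one lesser ambiguity. Severity is minor. The primary decision rules in 4.5.2 are clear, and primary tests, alpha and power are unaffected.

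A reader might take the reversal at 9 imputed Test eyes as the size of the trigger error. The documents do not support that. The figure shows how fragile any worst-case imputation is at a 0.8% event rate and when a tipping-point analysis would be wanted; nothing in the documents gives a chance that the analysis would actually be omitted. Nor do they support reading the plan as having dropped slit-lamp from the tipping-point analyses.

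The analysis-set effect is expected to be small, and the deposits effect close to nil unless exactly grade 2 is imputed and scored as success. The observed-value conflict has a 6.5% to 8.6% chance of arising with independent eyes, which is the SAP's working assumption, and 26% to 29% at the extreme where a subject's eyes always agree. These figures rest on the planned rates and on the assumed numbers of missing and undispensed subjects; the plan itself gives only losses of up to 10%.

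**What to change.** In SAP 4.5.3:
- **Trigger:** change *primary efficacy analysis* to *primary analysis* in both places, so that all four endpoints are covered.
- **Slit-lamp analysis set:** state that the best/worst-case and tipping-point analyses for slit-lamp use the Safety Population by treatment received; keep ITT for the three efficacy endpoints.
- **Deposits:** define the worst response as a grade greater than 2.
- **Slit-lamp worst response:** state that it is Present whether or not such a finding was observed in that group.

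The cost is about four sentences in the SAP. No new data are needed and no primary analysis changes.

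### The tipping-point algorithm for comfort and vision sets no 0-100 bound, so imputed scores can leave the scale and the tipping dataset can understate how low in-scale Test scores must go

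*SAP*

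**What the plan says.** SAP 4.5.1 sets the range: "overall comfort will be assessed for each eye on a scale from 0 to 100, with 100 denoting the most favorable response". Vision has the same range.

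SAP 4.5.3 gives the continuous tipping-point algorithm in full.

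- **Start, no scheduled follow-up visit observed:** the eye's endpoint "will be imputed using the observed group (i.e. Test or Control) mean".
- **Start, some visits observed:** "all visit-specific missing values for the given eye will be imputed using the observed eye-level mean".
- **Direction:** in its worked example the algorithm "will iteratively impute better and better scores within the Control group (and worse and worse scores within the Test group"). The example describes its starting result as a rejection of non-inferiority. I read this as rejection of the null hypothesis, so that non-inferiority was concluded, because otherwise the shift would move away from a tip.
- **Stop:** the only stopping rule is a reversed conclusion ("continue to perturbate the imputed values by increments 0.005 until the tipping point is reached").
- **Output:** the tipping dataset's group means "and the estimated difference in group means, will be reported".

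The analysis is conditional. It runs only if the observed-cases "conclusion is different than either the best-case or worst-case imputation conclusion". Those two scenarios stay inside the scale because they use observed extremes. The worst case, for example, "imputes the best response observed in the control group for the missing responses in control group".

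**The concern.** A tipping-point result is read by asking whether the imputed values at the tip are believable. If some of them cannot occur, that judgement is made on an invalid dataset. When non-inferiority was first concluded, any part of the Control shift beyond 100 does work that in-range Control scores could not do. The Test scores then need to fall less than they would if both arms stayed on the scale.

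The planned output does not reveal this. Group means average the imputed values with a much larger number of observed ones, so they look ordinary even when the imputed Control value is well above 100. The best- and worst-case analysis in the same section respects the scale, so the missing bound looks like an omission rather than a choice.

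**Working it through.** **Inputs.** Margin -5 (SAP 4.5.2.2); one-sided alpha 0.025 (SAP 4.1.1); SD 13.264 for comfort and 11.7 for vision, true difference 0 (SAP 2.2.1, 2.2.2); 680 eyes enrolled 1:1, so n = 340 per arm (SAP 1.2.2, 2.2.6). **Assumptions not in the documents:** the Control mean m and the share f of eyes wholly missing, taken as equal in both arms. The enrollment target allows for losses of up to 10%.

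**1. The plan's own figure.** With 300 eyes per group, the comfort SE is 13.264 × √(2/300) = 1.083. The noncentral t gives power of 0.996 for comfort and 0.999 for vision, consistent with the stated 99%.

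**2. Shift needed to tip.** Assume an observed difference of 0, with wholly missing eyes starting at the group mean and each arm moved by D.

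- Difference = -2fD
- Variance per arm ≈ (1-f)·SD² + f(1-f)·D²
- SE = √(2 × variance / 340)
- Solve -2fD - 1.96·SE = -5. The site and lens-group factors are ignored.

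Comfort, f = 5%, D = 28.45:

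- Difference = -2 × 0.05 × 28.45 = -2.84
- Variance = 0.95 × 175.93 + 0.0475 × 809.4 = 205.6
- SE = √(2 × 205.6/340) = 1.100
- Limit = -2.84 - 2.16 = -5.00

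| f | D, comfort | Control stays ≤ 100 only if m ≤ | D, vision |
|---|---|---|---|
| 3% | 45.3 | 54.7 | 47.9 |
| 5% | 28.4 | 71.6 | 30.2 |
| 10% | 15.0 | 85.0 | 15.9 |
| 15% | 10.3 | 89.7 | 10.9 |
| 20% | 7.9 | 92.1 | 8.4 |

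The fewer eyes are missing, the further each imputed value must travel.

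**3. Effect of a cap.** Comfort, f = 5%, m = 85 (assumed). Capped, Control stops at 100 (a shift of 15) and Test must move 41.2.

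| | Control imputed | Test imputed | Group means | Difference |
|---|---|---|---|---|
| Uncapped | 113.4 | 56.6 | 86.42, 83.58 | -2.84 |
| Capped | 100 | 43.8 | 85.75, 82.94 | -2.81 |

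At f = 3% and the same mean, uncapped Control is 130.3 and Test 39.7; capped, Test must fall to 12.6. At f = 10% the cap does not bind (Control 99.96). Over means of 60 to 90 and f of 3% to 20%, for both endpoints, the cap moved the difference by at most 0.16 point, and a tip was always found within the scale.

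**4. Partly observed eyes.** Only the missing visit moves, starting from the eye's own mean. With one of four visits imputed at 113 and three observed at 85, the eye average is (113 + 3 × 85)/4 = 92. The endpoint is in range although one imputed score is not.

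**5. How often, under assumptions.** A simulation of the algorithm used 170 subjects per arm, four visits, dropout plus missed visits, and 120 runs per setting. It counted triggered analyses that began from non-inferiority and had at least one imputed Control visit score above 100.

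- Control mean 80 to 90: 94% to 100%
- Control mean 70: 77% to 95%
- Control mean 60: 16% to 83%

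The trigger fired in 10% to 23% of runs with about 2% of eye-visits missing, 36% to 71% at 4%, and at least 90% at 7% and above. The score distribution, between-eye correlation and visit noise were assumed, and few runs were triggered at 2%.

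**The case against.** The strongest reply starts from the trigger. If non-inferiority was concluded and the worst case overturned it, a reversal with observed, in-range values has already been shown in a separately planned analysis. A reader might infer that the missing bound leaves it unknown whether tipping is possible inside the scale, or that it makes a fragile result look robust. The documents do not support either inference. The failed worst case settles the first. On the second, the cap makes the required Test scores more extreme, so judged on those scores the uncapped dataset makes the result look less robust, not more. This part of the reply stands.

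A reader might also infer that impossible Control scores will usually occur because scores sit near the top of the scale. Neither document gives an expected mean for comfort or vision, or a rate of missing visits. At 10% of eyes wholly missing, wholly imputed Control comfort values stay in range for any mean up to about 85. The direction is conditional too: Control moves up only after a conclusion of non-inferiority.

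Finally, the reported difference barely changes, and the analysis plays no part in the success rule. Both points are correct and keep the matter minor. They do not supply the missing bound. SAP 4.5.3 says it follows the spirit of a published method, but it then writes out its own algorithm without a limit.

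**Conclusion.** The point holds as a gap in the specification. As written, the comfort and vision algorithm can impute scores outside 0 to 100, above 100 in Control or in Test depending on which conclusion came first. The thresholds of about 85 (10% of eyes wholly missing) and 72 (5%) for comfort rest on no observed difference, the planning SD, 340 eyes per arm and equal missingness; those for vision are about 84 and 70. Frequency cannot be stated from the documents alone.

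The consequence is limited. In the 5% example with an assumed mean of 85, the reported difference moves by 0.03 point, but the Test score needed for a tip within the scale is about 44 rather than the 57 that the uncapped dataset implies. The planned output would not show that gap. This is a minor correction to a conditional sensitivity analysis.

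**What to change.** Add to the continuous-outcome algorithm in SAP 4.5.3:

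- Imputed values are held at 0 and 100.
- Once the imputed values in one arm reach their bound, the other arm continues to shift until the conclusion changes.
- The shift applied in each arm and the number of imputed values at a bound are reported with the group means and their difference.

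No rule for a search that ends without a tip should be needed when a failed worst case triggered the analysis, because full shifts to 0 and 100 are at least as extreme as that worst case. The cost is one or two SAP sentences, a small change to the program and two extra entries in the output. Sample size, data collection and the primary analysis are unchanged.
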